7.2.1 Quantitative Sensory Testing (QST)

We will perform a battery of psychophysical pain tests in the patients from Aim 1. The overall objective of the tests is to evaluate pain processing at different levels of the neuraxis. We will assess generalized mechanical sensitivity using the Multimodal Automated Sensory Testing (MAST) device. We will assess spinal segmental sensitivity using a vibrometer and a pressure algometer. We will assess temporal summation (TS) using a pointed skin probe. We will assess descending pain inhibition using the test of conditioned pain modulation (CPM). We will conduct all tests, including patient familiarization and training. For each test, we will read scripted instructions to the patients, and we will advise them that they can stop testing at any time without penalty if the sensations become intolerable.

7.2.1.1 Generalized Mechanical Sensitivity. We will assess generalized mechanical sensitivity using the MAST device.⁴⁰ The device consists of: 1) a wireless, hand-held thumbnail pressure stimulator with a circular 10 mm² rubber tip, 2) client interface displaying a pain-rating scale, and 3) a clinician interface used to design and control testing paradigms and generate data reports (**Figure 2A**). In this study, we will use the MAST device to deliver mechanical stimuli in the form of a series of automated (ascending) pressures onto the thumbnail bed (**Figure 2B**).

[figure not shown]

Figure 2. Generalized mechanical sensitivity assessed using the MAST system. (A) MAST system components: thumbnail pressure stimulator, patient interface displaying a pain-rating scale, and clinician interface used to design and control testing paradigms and generate data reports. (B) Close-up view of the thumbnail pressure stimulator.

First, we will apply 1-2 light “sample” pressures to the participant’s thumbnail to ensure proper thumb positioning. Once the subject’s thumbnail is in the proper position, we will conduct the familiarization procedure. We will apply a series of discrete pressure-pain stimuli to the subject’s left or right thumbnail. After each pressure is released, we will ask the subjects to rate their pain on a VAS or a 0-100 numerical rating scale (NRS), with 0 representing “no pain” and 100 representing “worst possible pain”. If any pressure is intolerable, subjects are allowed to let us know and the pressure will be released immediately. Subjects can also release the pressure themselves by pressing the ‘STOP’ button on their screen. Following familiarization, we will conduct the MAST ascending test, where we will apply an ascending series of discrete pressure stimuli with a duration of 2.5-5 s beginning at 0.25 kg/cm^2 and increasing in $0.25\text{-}0.50 \text{ kg/cm}^2$ steps to the subject’s opposite thumbnail. We will ask the subjects to rate their pain using a VAS or a 0-100 NRS. Testing is completed when a pain rating >80 using a VAS or a 0-100 NRS is received or after 10 kg/cm^2 of pressure has been applied. The MAST system will calculate, in kg of force, the patient’s pain detection threshold, tolerance, and moderate and high supra-threshold pain values. Following this test, a second series of tolerable pressures (as determined from the MAST ascending test) may be delivered in a random order. **Note:** This paradigm may require minor modifications during the execution of this protocol. These modifications will not exceed the parameters described above, i.e. maximum pressure intensity will never exceed 10 kg/cm^2 .

7.2.1.2 Spinal Segmental Sensitivity. We will assess spinal segmental sensitivity using a manual vibrometer⁴¹ and a pressure algometer^{33,42} at the primary pain site (**Figure 3**). The primary pain site is defined as the area of maximum pain intensity (i.e. the area of worst possible pain) as reported by the patient. If severe hyperalgesia or allodynia prevents testing of the primary pain site, we will select an adjacent, less sensitive pain area. We will also perform testing at mirror sites (site directly opposite to the tested pain site) and/or bilaterally at several control sites (e.g. trapezius, lateral epicondyle, forearm). We will perform testing with the subject resting in a stationary position (e.g. sitting, supine, prone) to reduce the possibility of postural compression of the nerves being tested.

We will use a handheld vibrometer (VSA-3000, Medoc Inc., Ramat Yishai, Israel) with a 1 cm^2 circular probe (**Figure 3 (A)**) to deliver vibratory, non-painful stimuli to determine sensitivity to vibration. We will apply an ascending series of vibratory stimuli. Subjects will report the first sensation of vibration (denoted as vibratory threshold). We will average the vibratory thresholds across two or three consecutive trials at each site separated by intervals of approximately 20 to 60 seconds. We may also apply a random sequence of fixed intensity vibratory stimuli, 1-3 times each, to the individual sites.

[figure not shown]

Figure 3. Spinal segmental sensitivity assessed using a (A) Vibrometer and a (B) Algometer. TS is assessed using a (C) PinPrick stimulator.

We will use a handheld, analog pressure algometer (FPK Algometer, Wagner Instruments, Greenwich, CT) with a 1 cm^2 flat rubber probe (**Figure 3 (B)**) to deliver pressure-pain stimuli. We will increase the pressure at a rate of approximately 0.30 kg/cm^2 or $30\text{-}50 \text{ kPa/s}$ (100 kPa/s maximum rate),

to a maximum of 10 kg/cm². Subjects will report their first sensation of pain (pressure-pain detection threshold) and pressure-pain tolerance. We will average the pressure-pain thresholds and pressure-pain tolerance across two or three consecutive trials at each site separated by intervals of approximately 20 to 60 seconds. We may also apply a random sequence of fixed intensity pressures, 1-3 times each, to the individual sites. We will ask the subjects to report the pain intensity of the pressure stimuli using a VAS or a 0-100 NRS.

7.2.1.3 Temporal Summation (TS). We will use a handheld, pointed skin probe (PinPrick Stimulator, MRC Systems, GmbH) to deliver a fixed intensity stimulus to evaluate TS (**Figure 3 (C)**). TS refers to an increased perception of pain in response to sequential stimuli of equal physical strength. It is a QST model of neural plasticity and central hyper-excitability that is thought to reflect the progressive increase in neuronal firing of dorsal horn neurons in response to repetitive nociceptive C-fiber stimulation (i.e. windup).²⁸ We will apply a single fixed intensity stimulus (256 mN or 512 mN) using the pointed skin probe perpendicular to the subject's skin for approximately 0.5 seconds. Following a 5-second pause, we will apply a train of 10 identical stimuli (256 mN or 512 mN) with a frequency of 1 Hz within an area of 1 cm². Immediately following the single stimulus and the train of 10 stimuli, we will ask the subjects to report the pain intensity of the stimulus using a VAS or a 0-100 NRS. We will conduct this testing paradigm (a single stimulus followed by a train of 10 stimuli) 3 times with the same 256 mN or 512 mN stimulator, and each cycle will be separated by at least 10 seconds. For each testing site (pain site and control site), we will divide the mean pain rating of the 3 stimulus trains by the mean pain rating of the single stimuli to calculate a wind-up ratio (WUR); a WUR of >1 indicates temporal summation. At 15- and 30-seconds following the last train of 10 stimuli, we will ask subjects to rate any residual pain sensation in the testing area using the 0-100 NRS.

7.2.1.4 Conditioned Pain Modulation (CPM). We will use CPM to test the effect of a noxious "conditioning" stimulus on a "test" stimulus to determine the efficiency of (supraspinal) descending pain inhibition. We will use pressure delivered by the algometer as the test stimulus, and a contralateral thumbnail pressure (using MAST) as the conditioning stimulus. We will determine pressure-pain thresholds before and after application of a conditioning stimulus. The conditioning stimulus is a 60-second continuous pressure to the contralateral thumbnail at the exact or similar pain intensity as the test stimulus. During the first 30-s, subjects will rate the intensity of the thumbnail pressure alone on a VAS or a 0-100 NRS. Parallel to the last 30-seconds of CPM conditioning while the subjects' thumb is still in the MAST device, we will reapply the test stimulus and determine pressure-pain thresholds. We will conduct the CPM test separately on the pain site and the control site. We will evaluate CPM as the mean difference in pressure-pain thresholds before and after application of a conditioning stimulus. If the difference in pressure-pain threshold is found to be negative, the subject is considered to have achieved an inhibitory CPM response; if the difference in pressure-pain threshold is found to be zero or positive, it is concluded that the subject did not exhibit a CPM response.

7.2.1.5 Other important considerations. If the participant has been diagnosed with peripheral neuropathy in the upper extremity that could potentially interfere with the MAST results, we will skip the MAST and thumb-based CPM procedures. However, the participant will complete the other tests. If the participant has a missing, severely malformed, or injured thumb on which testing is to be performed, we will conduct MAST testing on the opposite thumb, provided it is not missing nor injured. For example, we would conduct both familiarization and testing on the dominant thumb if the non-dominant thumb was abnormal, or vice-versa. To permit sufficient tissue recovery, we will provide a rest interval of 5-10 minutes between the MAST familiarization protocol and the MAST test, if we conduct testing on the same thumb. We will record the thumb on which familiarization and testing occurred. If

both thumbs are missing and/or injured, we will skip the MAST and the thumb-based CPM tests. However, the participant will complete the other tests.

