5. SPECIFIC AIMS/HYPOTHESES

5.1 To identify the treatment effects of Burst-SCS (Aim 1).

The goal of this aim is to determine the **pain-relieving effects of Burst-SCS**. In a randomized, double-blind, placebo-controlled, crossover study, we will compare the pain-relieving effects of Burst-SCS to sham (no) SCS in patients receiving Burst-SCS as part of their standard clinical care for chronic pain management. The primary outcome measure will be the change in patient-reported ratings of pain intensity (measured by the Visual Analog Scale, VAS).¹⁴ Secondary outcome measures will be related to the change in patient-reported ratings of pain quality [(measured by Pain Disability Index (PDI)²³ and Short Form McGill Pain Questionnaire (SFMPQ)],²⁴ pain severity (measured by Brief Pain Inventory, BPI),²⁵ pain spread (measured by Michigan Body Map, MBM),²⁶ and pain centralization (measured by Fibromyalgia Survey Criteria, FSQ).²⁷ Exploratory outcome measures will be related to the change in patient-reported ratings of affect (depression, anxiety), fatigue, sleep interference, catastrophizing, physical function, and overall quality of life. **We hypothesize that Burst-SCS will provide superior pain relief in patients as compared to sham SCS.**

5.2 To identify the therapeutic mechanisms of Burst-SCS (Aim 2).

The goal of this aim is to determine the **potential therapeutic mechanisms of action of Burst-SCS**. We will perform detailed clinical testing in the patients from Aim 1 using a series of quantitative sensory testing (QST) measures. We will assess sensitivity to non-painful vibratory stimuli and painful pressure stimuli. We will assess pain perception in response to sequential stimuli of equal physical strength (temporal summation or TS).²⁸ We will also determine the efficiency of (supraspinal) descending pain inhibition by measuring pain thresholds subsequent to the application of an acute conditioning stimulus (conditioned pain modulation or CPM).^{29,30} **We hypothesize that patients who respond to Burst-SCS will show decreased vibration and decreased pressure-pain sensitivity, reduced TS, and improved inhibitory CPM. Alternatively, patients who do not respond to Burst-SCS will demonstrate no changes or worsening of QST outcomes.**

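### Pressure tolerance and supra-threshold values are right-censored at 10 kg/cm², and the plan does not say how a run that ends at the limit is recorded or analysed

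*Combined protocol and SAP*

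**What the plan says.** Section 7.2.1.1 gives the MAST ascending series two end rules, in these words: "completed when a pain rating >80 using a VAS or a 0-100 NRS is received or after 10 kg/cm^2 of pressure has been applied". This limit is absolute, since any later change to the paradigm must respect that "maximum pressure intensity will never exceed 10 kg/cm^2". From this series the MAST system is to calculate "pain detection threshold, tolerance, and moderate and high supra-threshold pain values".

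Section 7.2.1.2 runs the algometer "to a maximum of 10 kg/cm²". Two endpoints come from it: "Subjects will report their first sensation of pain (pressure-pain detection threshold) and pressure-pain tolerance". The scoring is a plain mean: "We will average the pressure-pain thresholds and pressure-pain tolerance across two or three consecutive trials at each site".

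Aim 2 (section 5.2) predicts that responders "will show decreased vibration and decreased pressure-pain sensitivity, reduced TS, and improved inhibitory CPM". Table 1 in section 8.2.2 lists all QST measures as exploratory. Section 8.2.1 provides for distributional checks, transformations and outlier removal. Section 8.3.2 leaves the choice of test for the Burst-sham comparison open and adds correlations between pain intensity and QST. None of these sections mentions a value at the limit of the test. Section 14.2.3 presents the limit as a safety measure.

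**The concern.** A MAST run that ends because the rating passed 80 locates the patient's high-pain pressure. A run that ends because 10 kg/cm² was delivered, with a highest rating of say 55, does not: the high supra-threshold value and the tolerance are known only to be at least 10. A moderate value reached on the way up is still observed. The same holds for an algometer trial that ends at 10 with no tolerance reported.

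These are right-censored observations, and the plan treats them as ordinary measurements. The two handlings most likely in practice are to enter 10, which is too low, or to treat the value as missing, which removes the patient's Burst-sham pair. Averaging hides the problem: algometer trials of 9, 10 (limit) and 10 (limit) give 29/3 = 9.67, which looks observed but is only a lower bound.

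The error need not cancel between periods. Aim 2 expects pressure-pain sensitivity to fall in responders, so if the hypothesis is true more runs end at the limit under Burst than under sham. Both handlings then pull the contrast toward zero. The planned correlations would use the same compressed values.

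**Working it through.** **The plan's own figures.** There is nothing to reproduce. Section 8.1 gives 20 patients without alpha, power, SD or effect size, and no section gives a tolerance distribution or an expected share of patients at the limit. The inputs below are therefore assumptions, apart from the limit c = 10 kg/cm² and n = 20.

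**Model 1: same gain for every patient.** Patient tolerance t is Normal(μ, SD²). Sham = t + N(0, 1). Burst = t + gain + N(0, 1). Each visit's value then has SD s = √(SD² + 1).

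With capped runs scored as 10, the mean recorded value for a visit with true mean m is

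E[min(X, c)] = m·Φ(a) − s·φ(a) + c·(1 − Φ(a)), where a = (c − m)/s,

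and the share capped is 1 − Φ(a).

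Example, μ = 7, SD = 3, gain 1: s = √10 = 3.162.
- Sham: a = 3/3.162 = 0.949. Mean = 7(0.8286) − 3.162(0.2544) + 10(0.1714) = 6.710; 17% capped.
- Burst: a = 2/3.162 = 0.632. Mean = 8(0.7365) − 3.162(0.3266) + 10(0.2635) = 7.494; 26% capped.
- Recorded gain = 7.494 − 6.710 = 0.784, a loss of 22%.

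All scenarios (the column for dropped pairs is from simulation of 400,000 patients):

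| μ / SD | True gain | Capped, sham | Capped, Burst | Gain, scored as 10 | Loss | Gain, capped pairs dropped |
|---|---|---|---|---|---|---|
| 5 / 2 | 1 | 1% | 4% | 0.98 | 2% | 0.97 |
| 5 / 2 | 2 | 1% | 9% | 1.92 | 4% | 1.92 |
| 6 / 2.5 | 1 | 7% | 13% | 0.90 | 10% | 0.94 |
| 6 / 2.5 | 2 | 7% | 23% | 1.72 | 14% | 1.87 |
| 7 / 3 | 1 | 17% | 26% | 0.78 | 22% | 0.92 |
| 7 / 3 | 2 | 17% | 38% | 1.47 | 27% | 1.83 |
| 8 / 3 | 1 | 26% | 38% | 0.68 | 32% | 0.89 |
| 8 / 3 | 2 | 26% | 50% | 1.24 | 38% | 1.78 |

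Dropping pairs biases less here but costs data: in the 7/3, gain 1 case it removes 28% of pairs, about 6 of 20.

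Power of a paired t-test at n = 20, two-sided 0.05, gain 1, capped runs scored as 10: about 85% without a limit, against 85% (5/2), 82% (6/2.5), 77% (7/3) and 70% (8/3). For a gain of 2 it stays above 99% throughout.

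**Model 2: gain varies between patients.** SD 2, within-patient correlation 0.7, mean gain 1, indexed by the share capped under sham:

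| Capped under sham | Effect kept, scored as 10 | Power, scored as 10 | Effect kept, pairs dropped | Power, pairs dropped |
|---|---|---|---|---|
| 0% | 100% | 78% | 100% | 78% |
| 5% | 92% | 76% | 91% | 67% |
| 10% | 85% | 73% | 86% | 58% |
| 30% | 61% | 61% | 75% | 31% |

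At 10% capped under sham, 38% of the quarter with the largest gains sit at the limit under Burst, against 9% of the quarter with the smallest.

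**Does a censored analysis repair it?** A paired bivariate-normal censored likelihood, fitted to 300 simulated trials of 20 patients with true gain 1.0, gave mean estimates of 0.99 (10% capped under sham) and 1.02 (30%). Scoring as 10 gave about 0.85 and 0.61. This is a favourable test, because the fitted model matches the one that generated the data.

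**The case against.** The strongest reply is that the size is unknown and may be trivial. At 5/2 the loss is 2% to 4%, and section 7.2.1.2 tests the site of worst pain and allows for severe hyperalgesia there, so frequent capping at that site cannot be presumed. This stands, and the point is conditional for that reason.

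A reader might infer that the patients Burst helps most are the ones mis-scored. The documents do not support that. Capping follows the level reached, not the gain: a patient with high tolerance under sham is capped with no benefit at all, and a sensitive patient with a large gain may never be. Model 1 gives everyone the same gain. In Model 2 large gainers are over-represented at the limit, but at 10% capped under sham most of them (62%) are not capped, and the simulated gain includes within-patient noise.

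A reader might also infer that the whole Aim 2 pressure effect shrinks. That is too broad. Detection thresholds from both devices lie below tolerance, CPM (section 7.2.1.4) is built on thresholds, and the optional fixed-intensity pressures are rated 0–100. Table 1 also lists generalized mechanical sensitivity separately from pressure-pain sensitivity, so MAST is not clearly the direct test of the Aim 2 pressure hypothesis.

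Nor does the plan prescribe scoring a capped MAST run as 10 or as missing. The software's calculation is not described and might truncate, extrapolate or flag. That supports writing the rule down.

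Finally, the screening in section 8.2.1 could reveal a pile-up at 10, and section 8.3.2 does not exclude a censored or rank method. True, but transformation and outlier removal cannot recover a value the test never reached. If the file holds only 10, a tolerance truly reported at the limit can no longer be told from a capped run.

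**Conclusion.** The concern holds in conditional form. MAST tolerance and supra-threshold values and averaged algometer tolerance are right-censored at 10 kg/cm², and no scoring or analysis rule covers this. If patients reach the limit, entering 10 or dropping the pair biases the Burst-sham contrast in these measures toward zero. With capped runs scored as 10 the loss is about 2% to 38% over the assumed range in Model 1, and nil if no one is capped. The loss of power under that scoring is modest except where capping is common; dropping pairs costs more.

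The documents do not establish that the effect will shrink, or that Aim 2 as a whole is compromised. The measures are exploratory and the study has 20 patients, so this is a correction worth making at low cost and no threat to the primary VAS comparison.

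**What to change.** Keep the 10 kg/cm² limit as it is. Change only recording and analysis.

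1. **Sections 7.2.1.1 and 7.2.1.2, at testing.** Flag each MAST run that ends at the limit without a rating above 80, and each algometer trial that ends there without a reported tolerance, as ≥10, censored. Set the flag from how the run ended, not from the number stored: MAST results are reported in kg of force while the limit is in kg/cm². State what the MAST software returns for such a run.
2. **Algometer averaging.** Do not average a capped trial as an observed 10. Either enter the trial as censored in the model, or treat the site average as a lower bound. Apply the same rule whether two or three trials are run.
3. **Section 8.3.2.** Compare Burst with sham on tolerance and supra-threshold values with a within-patient censored (Tobit-type) model, or a paired rank or sign comparison in which capped outranks uncapped and a pair capped in both periods is a tie.
4. **Reporting.** Give the number of capped runs under Burst and under sham.
5. **Optional support.** Add the mean MAST rating over pressures delivered at both visits 4 and 5. This needs the same step size at both visits, because section 7.2.1.1 allows 0.25 to 0.50 kg/cm².

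The cost is one flag in the QST file, a few sentences of plan text and slightly more analysis work, with no new tests, visits or patients. Pairs capped in both periods will carry little information under either method.

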8. STUDY STATISTICS AND DATA ANALYSIS PLAN

8.1 Sample Size

For this study, we will recruit **20 chronic pain patients** for whom Burst-SCS has been recommended as a treatment option as part of their standard clinical care.

8.2 Data Analysis Plan

8.2.1 Initial data screening.

Prior to any of the substantive analyses, we will evaluate the data to ensure that it has appropriate variability and distributional properties for the subsequent analyses. When necessary and sensible, we will consider data transformations, including the elimination of outliers and the reduction of non-linearity and non-normality, for variables with problematic properties.

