3. STUDY BACKGROUND

Chronic pain is a major health problem in the United States and affects ~100 million American adults.¹ Patients with chronic pain have ~3 times higher healthcare costs as compared to healthy individuals.² Chronic pain is debilitating as it impacts most aspects of a person's life, including physical inability, emotional distress and/or psychological impairment. Due to its debilitating nature and widespread impact, chronic pain is complex and often challenging to treat. Unfortunately, conventional treatments (e.g. pharmacological therapies, surgery) have limited effectiveness for many people with severe chronic pain.² Therefore, less conventional forms of therapy, such as neurostimulation are often considered for these patients.^{3,4} **Spinal cord stimulation (SCS)** is one such popular neurostimulation therapy frequently utilized for patients with chronic pain conditions that are often refractory to conventional treatments (e.g. failed back surgery syndrome and complex regional pain syndrome).^{3,5,6} Typically, the procedure of SCS involves implanting an electrode array in the epidural space dorsal to the spinal cord via a percutaneous needle or through the performance of a laminectomy.^{7,8} The electrode array is connected to an implantable pulse generator that produces an electrical stimulus. The success of SCS is determined by its ability to deliver electrical stimulation to the dorsal columns of the spinal cord in an attempt to create analgesia (or inability to feel pain).^{9,10} However, SCS has shown only limited success rates in treating patients with refractory chronic pain.^{5,11} The success rate of SCS, defined as the proportion of patients receiving 50% or greater pain relief, is approximately 58%.¹¹ Furthermore, the success rate of SCS varies widely across studies, often declines over treatment time, and significant pain relief does not necessarily translate to improvements in quality of life (e.g. patients can't go back to work).^{6,11-13} Therefore, there is a growing need for the development of improved neurostimulation treatments in chronic pain.

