Burst spinal cord stimulation (Burst-SCS) is an exciting new SCS therapy that has the potential to transform neurostimulation treatments in chronic pain. **Burst-SCS was approved by the United States Food and Drug Administration (FDA) in 2016 to treat chronic intractable pain of the trunk and/or limbs, including unilateral or bilateral pain associated with any one of the following: failed back surgery syndrome and intractable low back and leg pain.** Burst-SCS system delivers packets of high-frequency electrical pulses (500 Hz) periodically to the spinal cord (40 times a second) as compared to conventional SCS that deliver a constant stream of low-frequency pulses (~50 Hz).^{14,15} A recent large clinical trial (SUNBURST; Success Using Neuromodulation with BURST) reported Burst-SCS to be more effective than conventional SCS in relieving pain.¹⁶ Although findings of this trial suggest the potential superiority of Burst-SCS over conventional SCS, other studies have reported variable outcomes.^{14,15,17-21} Furthermore, a majority of these clinical studies were performed in an unblinded manner.^{14,17,18,21} Therefore, we believe that a "placebo" effect likely confounded the findings of these studies and the resulting variability in outcomes. Comparing the effects of Burst-SCS to sham (no) SCS in a randomized, double-blind, placebo-controlled, crossover fashion will help systematically control for placebo effects and will help identify the true pain-relieving effects of the therapy. We also believe the variable outcomes with Burst-SCS is attributed to our poor understanding of its mechanisms of action. Currently, there is minimal scientific understanding of how Burst-SCS works to relieve pain. Preliminary evidence suggests that Burst-SCS may provide improved pain relief via different therapeutic mechanisms of action relative to conventional SCS.²² However, such claims are anecdotal and remain to be validated. To better understand the mechanisms of action of Burst-SCS, we will adopt a mechanistic approach to Burst-SCS.

As such, the proposed study will determine the treatment effects of Burst-SCS and its associated therapeutic mechanisms of action by systematically controlling for placebo effects.

Understanding the treatment effects of Burst-SCS and its associated therapeutic mechanisms can provide useful information to help conduct larger clinical studies in the future. Because Burst-SCS

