6.5 Blinding

We will have **two** research teams. **One team will be unblinded** (e.g. clinical care provider/company representative, study coordinator) and will perform stimulator programming/adjustment, and the **other team will be blinded** (e.g. research personnel) and will perform clinical testing and collect study outcome measures.

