8.2.2. Defining the variables of interest

Table 1. Variables of interest

Treatment Outcomes
Primary outcome: VAS ratings
Secondary outcomes: Self-reported patient questionnaires (SFMPQ, PDI, BPI, MBM, FSQ)
Exploratory outcomes: Self-reported patient questionnaires (PainDETECT, EQ-5D, HADS, CSQ, PROMIS SD), QST measures (generalized mechanical sensitivity, vibration sensitivity, pressure-pain sensitivity, TS and CPM)

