8.3 Data analysis

8.3.1 Treatment outcomes

We will compute VAS scores at pre-implantation (visits 1 and 2) and post-implantation (visits 3,4 and 5) to help assess percentage change in pain scores due to the effects of stimulation (Burst-SCS and sham SCS). We will also compare our VAS ratings to other clinical results available in the literature. Similarly, we will assess outcomes of pain-specific questionnaires at pre-implantation and post-implantation, and compare across all patients using appropriate statistical tests.

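### Section 8.2.1 allows outliers to be eliminated without exempting the primary VAS or requiring masking, and in a 20-patient crossover deleting genuine ratings can shrink the Burst-sham effect even under mask

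*Combined protocol and SAP*

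**What the plan says.** Section 8.2.1 (Initial data screening) states that before the substantive analyses "we will evaluate the data to ensure that it has appropriate variability and distributional properties for the subsequent analyses". It continues, under a condition of necessity and good sense: "we will consider data transformations, including the elimination of outliers and the reduction of non-linearity and non-normality, for variables with problematic properties". No numerical criterion is given for an outlier or for a problematic property, and no analysis with all values kept is planned alongside.

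Table 1 in section 8.2.2 follows directly and lists "Primary outcome: VAS ratings" among the variables of interest, with no exemption from the screening rule. Section 8.3.1 names no test for the VAS. For the questionnaires it says only that the team will "compare across all patients using appropriate statistical tests".

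On masking, section 6.5 blinds the team that "will perform clinical testing and collect study outcome measures". Neither it nor section 6.4 (Randomization) mentions whoever screens or analyses the data.

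On how varied response may be, section 3 says "The success rate of SCS, defined as the proportion of patients receiving 50% or greater pain relief, is approximately 58" per cent, that "the success rate of SCS varies widely across studies", and, of burst stimulation, that "other studies have reported variable outcomes". Section 5.2 frames its hypotheses separately for patients who respond and patients who do not.

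**The concern.** In most data sets an outlier rule is meant to catch mistakes. Here an extreme VAS rating may be the effect under study. If a minority of patients respond strongly to Burst-SCS, their low ratings make the VAS distribution skewed, and that skewness is what a distributional check would flag. The values then open to deletion are the true responses.

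The design adds leverage. Each patient supplies one Burst-sham contrast, so removing either rating removes the contrast. Two things are at stake:

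- **Bias.** Deleting genuine responses moves the mean contrast toward zero. Masking does not help, because a strong response can be extreme without its label.
- **Type I error.** If deletion is done on visible Burst-sham differences, removing extremes narrows the estimated spread and a nominal 5% test can reject too often.

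The point covers the VAS and the questionnaires. It leaves out the QST measures, where, for example, a wind-up ratio with a near-zero denominator is a scoring problem that keeping every value would not solve.

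**Working it through.** The plan gives no alpha, power, effect size or SD, so it has no figure of its own to reproduce.

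**Inputs from the documents.** 20 patients (section 8.1); two-period crossover (section 6.1); VAS on a 100 mm line (section 7.1.1).

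**Assumptions.** Paired t-test at two-sided 5%; 10 patients per sequence; 45 mm benefit over sham in responders and none in the others; within-group SD of the contrast 15 mm. Outlier rules are 2 SD, 3 SD or the 1.5×IQR boxplot fence. *Conditional* means that deletion happens only if Shapiro-Wilk gives p<0.05 on the screened variable, which is one reading of the plan's wording. *Always* means the fence is applied regardless.

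**Step 1: leverage by hand.** Take 5 responders at 45 mm and 15 patients at 0.

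- All values: 5 × 45 / 20 = 225/20 = 11.25 mm.
- One responder lost: (225 − 45)/19 = 180/19 = 9.47 mm, a loss of 1.78 mm.
- Two lost: 135/18 = 7.50 mm, a loss of 3.75 mm.

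**Step 2: how often it happens.** Simulation with 20,000 to 40,000 trials per setting; Burst minus sham, so negative favours Burst; 25% responders; conditional deletion under mask.

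| Screened variable | Rule | All values | After deletion | Loss | Power |
|---|---|---|---|---|---|
| Period differences | 2 SD | −11.2 mm | −10.8 mm | 0.4 mm | 47% to 46% |
| Period differences | boxplot | −11.2 mm | −10.6 mm | 0.6 mm | 47% to 45% |
| Pooled VAS: mean 60, SD 20, correlation 0.5 | 2 SD | −10.6 mm | −9.9 mm | 0.7 mm | 38% to 35% |
| Pooled VAS: mean 65, SD 20, correlation 0.7 | 2 SD | −10.8 mm | −9.8 mm | 1.0 mm | 47% to 40% |
| Pooled VAS: mean 70, SD 15, correlation 0.5 | 2 SD | −11.1 mm | −8.1 mm | 3.0 mm | 48% to 31% |

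The first two rows agree with a direct check. About 10% of those trials are touched and the estimate moves 4.5 to 6.5 mm in each, and 0.10 × 4.5 to 6.5 = 0.45 to 0.65 mm on average.

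**Step 3: is a normality check a safe filter?** On pooled VAS, Shapiro-Wilk fails in 5%, 11% and 6% of trials with no responders (the three settings in table order). With 25% responders it fails in 16%, 26% and 58%. The effect itself triggers the check.

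**Step 4: other responder shares, conditional deletion.** On period differences with the 2 SD rule:

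- 10% responders: −4.5 becomes −3.8 mm.
- 40% responders: −18.0 becomes −17.9 mm.
- 58% responders: under 0.1 mm is lost. On pooled VAS at this share, 0.1 to 1.1 mm is lost and power stays at 92% or more.

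A 3 SD rule costs about 0.3 mm or less on differences. On pooled VAS it costs 0.5 mm or less at 25% responders and up to 0.8 mm at 10%.

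**Step 5: type I error with no treatment effect.**

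- Visible Burst-sham differences, conditional: 5.8% (2 SD) or 6.0% (boxplot); 5.9% or 6.8% with t(4) errors.
- Masked differences or pooled raw VAS: 4.8 to 5.2%, conditional or always.
- Raw VAS screened within treatment, conditional: 5.0 to 5.4%.

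**Step 6: upper bound.** If the fence were always applied at 25% responders, the estimate on masked differences would be −8.4 mm (2 SD) or −7.8 mm (boxplot), with power about 34% or 32%. Pooled VAS with 2 SD would give −7.8, −7.9 and −6.6 mm. Visible differences would give a type I error of 9.9% or 8.9%.

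**The case against.** The clause is permissive: the team will only consider deletion, when necessary and sensible, and before the substantive analyses. On that reading most losses are a millimetre or less. The one large conditional loss depends on a single assumed setting. The documents support neither 25% responders, nor 45 mm, nor an SD of 15 mm, nor a Shapiro-Wilk trigger. All of this stands, and it limits the size of the point. It does not remove it: discretion over primary data without a criterion is the gap, and screening earlier is not the same as screening under mask.

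It is also fair that section 8.3.1 speaks of percentage change in VAS, whereas the working uses millimetre contrasts. A low baseline can make a percentage extreme. The figures above do not cover that case.

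Three stronger readings are tempting, and the documents do not support them:

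- **That screening will be done unmasked.** The plan is silent on who screens and what they see. Silence is a gap, not evidence of unmasked screening.
- **That type I error roughly doubles, or that a quarter or more of the effect is lost as a rule.** Those sizes come mainly from applying a fence automatically, which the conditional wording does not describe. Step 6 is a bound only.
- **That the 58% in section 3 makes the issue harmless.** It counts patients with 50% or greater relief under SCS in general, not relief beyond sham, so it does not fix the responder share for this contrast. Equally, nothing shows that the share is as low as 25%.

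**Conclusion.** The point holds in limited form. Section 8.2.1 leaves deletion of genuine primary VAS ratings open, with no criterion, exemption or masking requirement, and deletion can attenuate the Burst-sham effect even when done under mask. Under conditional deletion the expected loss is modest in most assumed settings and material in one. It is close to nil on differences when responders are the majority. Inflation of type I error is a separate and small risk that arises mainly when the screener sees signed Burst-sham differences. All sizes depend on the assumed response distribution, trigger and test. Confidence in the mechanism is high; confidence in the magnitude is not. The change is worth making because it is cheap and because keeping all valid values, with a rank-based or permutation check, handles extreme ratings without discarding patients.

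**What to change.** Keep section 8.2.1 as it stands for the QST measures, and add:

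> For the VAS and questionnaires, all valid values are analysed on their original scale in the primary analysis; a value is excluded only for a documented recording or device error, decided before treatment codes are merged. Any transformation or outlier exclusion for these outcomes is a sensitivity analysis only, and a signed-rank or permutation test of the Burst-sham VAS difference is reported as a sensitivity analysis.

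This also closes the discretionary transformation of the primary VAS, which striking the outlier phrase alone would leave open. If percentage change is to be a main summary, small baseline values need a rule of their own.

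The cost is two sentences of text, with no change to visits, conduct or sample size. Intervals are slightly wider when a genuine extreme value is kept. In the 25% responder case on differences, the 95% half-width is 11.4 mm with all values, against 11.0 to 11.1 mm with conditional deletion, and the narrower interval is centred on an attenuated estimate.
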